**Description of Study Design:**

Double blind, randomized, controlled, Phase 2 clinical trial in hookworm-unexposed adults living in the metropolitan area of Washington, DC. Subjects will receive three doses of the assigned vaccine formulation, or saline placebo, delivered intramuscularly on approximately Days 0, 56, and 112.

Subjects will be challenged with 50 infectious *N. americanus* larvae 4 weeks after 3rd vaccination. Subjects will be evaluated weekly starting 5 weeks post-challenge to assess infection status. Albendazole will be administered 20 weeks post-challenge to cure infections. Subjects will be followed until 10 months after their final vaccination.

Safety of vaccination will be measured from the time of each study vaccination (Day 0) through 14 days after each study vaccination by the occurrence of solicited injection site and systemic reactogenicity events. Safety of CHHI will be measured from the time of larval application (Day 140) through the first day of treatment with albendazole (Day 280).

Unsolicited non-serious adverse events (AEs) will be collected until approximately 1 month following each study vaccination and from study Day 140 (day of CHHI) through Day 297.

New-onset chronic medical conditions, Serious Adverse Events (SAEs), and Adverse Events of Special Interest (AESIs) will be collected from the time of the first study vaccination through approximately 10 months after the third study vaccination (final visit). Clinical laboratory evaluations for safety will be performed on venous blood collected approximately 14 days after each vaccination and CHHI.

Immunogenicity testing will include IgG antibody responses to Na-GST-1, by a qualified indirect enzyme-linked immunosorbent assay (ELISA), on serum obtained prior to each study vaccination and CHHI, and at time points after each vaccination and after CHHI (see Appendix A); the affinity of vaccine-induced antibodies against Na-GST-1 using Surface Plasmon Resonance; the functional activity of vaccine-induced antibodies via *in vitro* enzyme neutralization assay; antigen-specific memory B cell responses; and, the innate immune responses to each of the TLR receptor immunostimulants.

Parasitological testing will include microscopic fecal egg detection by a qualified saline flotation technique, fecal egg counts by the McMaster method, fecal PCR for hookworm DNA, and peripheral eosinophil counts.

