Hookworm transmission occurs when skin comes into contact with infective third-stage larvae (L3) in fecally contaminated soil. The L3 have the ability to penetrate the skin, usually of the hands, feet, arms, buttocks and legs. The L3 invade human tissues and enter the gastrointestinal tract where they molt to the adult stage approximately 5-9 weeks following initial host entry. Adult hookworms are approximately 1 cm long parasites that cause host injury by attaching to the mucosa and submucosa of the small intestine to produce intestinal blood loss. There is a direct relationship between hookworm intensity (as determined by fecal egg counts) and host blood loss; typically the presence of between 40 and 160 adult hookworms in the intestine results in blood loss sufficient to cause anemia and malnutrition. The term "hookworm disease" refers primarily to the iron deficiency anemia and protein losses that occur in moderate and heavy infections (4). When host iron stores become depleted, there is a direct correlation between hookworm intensity and reduced host hemoglobin, serum ferritin, and protoporphyrin. Because of their low iron stores, children and women of reproductive age are the populations considered the most vulnerable to hookworm-associated blood loss (4-11).

In children, chronic hookworm infection and the resultant iron deficiency anemia have been shown to impair physical and intellectual development (3, 12, 13). Preschool children are particularly vulnerable to the effects of hookworm anemia and disease (8). In addition to its health impact on children, hookworm infection also affects adults. Unlike other soil-transmitted helminth infections such as ascariasis and trichuriasis, in which the highest intensity infections occur almost exclusively in school-aged children, it has been shown that high-intensity hookworm infections may also occur in adults (14-16).

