## 2.1.9 Clinical Experience with Controlled Human Hookworm Infection (CHHI)

A total of nine experimental human hookworm infection studies have been reported in the literature and two more (EudraCT 2008-005008-24 and NCT01940757) are currently underway in the United Kingdom and Washington, DC, respectively (54-61). The completed studies were conducted to investigate the natural history of hookworm infection in humans but also to test the therapeutic efficacy of experimental infection on various inflammatory and allergic diseases such as celiac disease, inflammatory bowel disease and allergic rhinoconjunctivitis. The important points regarding these previous hookworm challenge studies are that: a) experimental infections were overall well-tolerated, with minimal significant adverse events; b) hookworm infection is curable with well-tolerated licensed medications; and, c) the time to patency (as determined by detection of egg in feces) is predictable. These studies, conducted under approvals from ethical review committees in the US, Australia and the UK, have enrolled a total of over 100 adults who have been challenged with between 10-100 infectious *N. americanus* larvae.

In the previous studies, the time until hookworm eggs were detectable by microscopic examination of feces was consistently between 4 and 8 weeks after challenge. All experimental infections were completely cured by administration of a benzimidazole anthelmintic drug (either albendazole or mebendazole) orally. The most common adverse effects of challenge infection in these studies included transient skin rash at the site of larval application and gastrointestinal discomfort beginning approximately 4 to 6 weeks post-challenge that was characterized by flatulence, abdominal pain, nausea, vomiting, and diarrhea.

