#### **5.3.4 Handling of Withdrawals**

The primary reason for withdrawal from the study will be recorded on the appropriate data collection form. Subjects will be encouraged to complete the Early Termination Visit. The Early Termination Visit procedures are listed in **Section 7.5**. Although subjects are free to withdraw at any time or may be withdrawn by the Principal Investigator or appropriate co-investigator at any time, subjects who receive at least one dose of study vaccine will be encouraged to remain in the study for follow-up safety assessments and collection of venous blood samples for immunogenicity testing and fecal samples for parasitological testing. Every attempt will be made to follow all adverse events, including solicited injection site and systemic reactions, serious adverse events, and new-onset chronic medical conditions ongoing at the time of early withdrawal to resolution.

Subjects who have received *N. americanus* challenge by CHMI who withdraw or are withdrawn before Day 280 post-CHHI and who have not been treated with albendazole for hookworm infection must receive early presumptive treatment for hookworm or else agree to continue be followed until Day 297 (Visit #37) post-CHHI. Subjects who elect to withdraw from the study will not be subjected to additional research portions of the study (research blood collections, fecal collections, etc.) although they will be strongly advised to continue with the safety portions (i.e., fecal testing for hookworm eggs, safety laboratory tests) of the study.

Although subjects are free to withdraw at any time or may be withdrawn by the Principal Investigator or appropriate co-investigator at any time, subjects will be encouraged to remain in this study for safety follow-up assessments (at a minimum, by telephone if not in person) continuing through approximately study Day 140 for subjects who do not receive CHHI, or study Day 189 (approximately 6 weeks post-CHHI) for subjects who receive CHHI. In the latter case, volunteers will be encouraged to remain in the study until Day 189 to ensure that treatment with albendazole is given after the point where the hookworms would have become adult worms, since the medication is not effective against the immature forms of the worm.

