## 7.5 Early Termination Visit

Every attempt will be made to retain subjects once they have been enrolled. However, if for safety reasons, withdrawal of consent, or loss to follow-up, a subject is deemed by the investigators and/or SMC to be not eligible to receive the study product as per protocol, he/she will discontinue vaccinations. Volunteers will be encouraged to continue attending scheduled study visits to be followed for safety. Study subjects who discontinue the vaccinations or study participation early will not be replaced. Withdrawal from the study for any reason will not impact the subject's medical care.

The following activities will be performed at the early termination visit for subjects who withdraw, or are withdrawn or terminated from the study:

- Obtain interim medical history by interview of subjects and note any changes since the previous visit.
- All concomitant medications will be recorded on the appropriate data collection form (if within 28 days of subject's last vaccination or during the CHHI phase of the study).
- Information regarding adverse events/Serious Adverse Events will be assessed and recorded on the appropriate data collection form.
- A targeted physical examination may be performed by a study clinician licensed to make medical diagnoses and listed on the Form FDA 1572 as the Principal Investigator or co-investigator, if indicated based on review of interim medical history.
- Approximately 10 mL of venous blood may be collected for safety labs and performed by the local clinical laboratory (if prior to Visit 15 and if not recently obtained per study schedule).
- Approximately 40 mL of venous blood may be collected for antibody and cellular assays (if prior to Visit 15 and if not recently obtained).

Subjects who have undergone CHHI and who insist upon terminating the study prematurely and prior to completion of Day 197 will be recommended to take albendazole for hookworm infection (400 mg orally for three consecutive days). Follow-up care will be offered regardless of study participation, if so desired by the subject.

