## 7.7 Clearance of Infection

In order to confirm that treatment with albendazole results in cure of experimental hookworm infection, participants will be asked to provide fecal samples 1, 1½ and 2 weeks following treatment (Days 290, 294 and 297), which will be examined for the presence of eggs by microscopy. Three negative samples are required as confirmation of successful treatment. As treatment with even a single dose of albendazole is currently highly effective (20, 71), and as this study is being conducted in a hookworm non-endemic area, cure following a 3-dose course of treatment is expected for all subjects (72). Nevertheless, if eggs are detected in post-treatment fecal samples, the participant will be given a second course of albendazole, with the same procedure for confirmation of successful treatment.

In addition, treatment with albendazole will be offered to any study participant who wishes to withdraw from the study (whether due to the occurrence of adverse events or for personal reasons) prior to study Day 280. In such an instance, the participant will be strongly encouraged to provide post-treatment fecal samples to ensure cure of the infection. Fecal samples at 1 week, 2 weeks and 60 days following albendazole treatment will be requested for subjects who terminate the study early.

If a female becomes pregnant during the course of the study, provisions for treatment of hookworm infection will be offered (i.e., albendazole treatment after the first trimester of pregnancy).

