## 14.6 Study Discontinuation

If the trial is discontinued, subjects who sign the informed consent form, and are randomized and vaccinated will continue to be followed for safety assessments. No further study vaccinations or CHHI will be administered.

In the event that the study is discontinued, all subjects who received CHHI and who have been and who have not been treated for hookworm will be offered albendazole (3 daily oral doses of 400 mg). The subjects will be asked to follow up weekly for 2 weeks to ensure clearance of infection (see **Section 7.7**).

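### After challenge, no exit route sets an earliest treatment time although the protocol says albendazole fails against immature worms, and the section 14.6 clearance checks can both precede the first detectable eggs

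*Protocol*

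**What the plan says.** All references are to the Protocol. Challenge (CHHI) is on study Day 140.

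- **Drug activity (5.3.4).** Challenged subjects who leave are encouraged to stay to Day 189, described as about six weeks after CHHI. The aim is that albendazole is given once the worms are adult, "since the medication is not effective against the immature forms of the worm".
- **Maturation (2.1.1).** After larvae enter the host, "they molt to the adult stage approximately 5-9 weeks following initial host entry".
- **Eggs (2.1.9).** In earlier challenge studies "the time until hookworm eggs were detectable by microscopic examination of feces was consistently between 4 and 8 weeks after challenge".
- **Withdrawal (5.3.4).** An untreated subject who leaves before Day 280 must either have early presumptive treatment or accept follow-up to Day 297. Both days are labelled post-CHHI.
- **Early termination visit (7.5).** Subjects who insist on leaving "prior to completion of Day 197 will be recommended to take albendazole for hookworm infection".
- **Clearance (7.7).** Albendazole is offered to anyone withdrawing before study Day 280. Three negative samples are needed to confirm cure. The standard samples come 1, 1½ and 2 weeks after treatment (Days 290, 294, 297). For leavers the schedule differs: "Fecal samples at 1 week, 2 weeks and 60 days following albendazole treatment will be requested for subjects who terminate the study early".
- **Study discontinuation (14.6).** Challenged subjects are offered albendazole. "The subjects will be asked to follow up weekly for 2 weeks to ensure clearance of infection", with a cross-reference to 7.7. General safety follow-up also continues.
- **End of contraception.** Section 2.3.1.2 and exclusion criterion 2 run it to documented clearance. Section 14.4 runs it to at least one month after clearance.

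**The concern.** The protocol states a biological reason why treatment timing matters, then describes four ways out of the study that do not carry it through. None gives an earliest treatment time, and the only safeguard, staying to Day 189, is encouragement. The clearance checks are timed from treatment and not from challenge. A negative stool taken before eggs could be present carries no information on whether treatment worked.

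These are deliberately infected volunteers, and 9 of 10 became infected at this larval dose in the earlier study (2.1.9.1). Clearance is also the event to which the end of contraception is tied. An early stop is foreseeable. One related SAE or AESI suspends further vaccinations and challenges pending review (9.5). The safety committee also meets after the first 20 subjects complete Day 175 and may recommend termination (9.7.2). Subjects challenged later than those 20 could then be less than 5 weeks past challenge.

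**Working it through.** **Inputs.** Challenge on Day 140 (Protocol Summary, Appendix A); adult stage 5-9 weeks = 35-63 days (2.1.1); eggs 4-8 weeks = 28-56 days (2.1.9); stool schedules from 7.7 and 14.6; 48 subjects, 6-month enrolment, 22-month study and 14-month participation (Protocol Summary).

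**1. The stated labels.** Weeks after challenge = (study day − 140)/7.
- Day 175: 35/7 = 5.0, and Day 280: 140/7 = 20.0. Both agree with the protocol's labels.
- Day 189: 49/7 = 7.0, against a label of about 6. Six weeks would be 140 + 42 = Day 182. The label fits if challenge falls on the last day of its window: (189 − 147)/7 = 6.0.
- Day 197: 57/7 = 8.1 weeks.
- Days 280 and 297 are labelled post-CHHI in 5.3.4 but are study days: 140 and 157 days after challenge.

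**2. Day 189 against maturation.** The stated range is Day 140 + 35 = 175 to 140 + 63 = 203. Day 189 is inside it, and so is Day 182. Staying to Day 189 therefore does not guarantee adult worms on the protocol's own figures.

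**3. Section 14.6.** Let t be days from challenge to first dose. The weekly checks fall at t + 7 and t + 14.
- Both before day 28 (earliest eggs) if t + 14 < 28, so t < 14 days (2 weeks).
- Both before day 56 (latest eggs) if t + 14 < 56, so t < 42 days (6 weeks).
- Example, t = 7: checks on days 14 and 21.
- Counting from the last of three daily doses adds 2 days, and the limits become 12 and 40 days.

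**4. If 14.6 means the standard 7.7 schedule.** Samples at 1, 1½ and 2 weeks end at t + 14, so the limit is again t < 14 days. On the listed study days the offsets from Day 280 are 10, 14 and 17, and t + 17 < 28 gives t < 11 days. Three negatives can then be collected before any egg is expected.

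**5. If the early-leaver schedule in 7.7 applies.** The last stool is at t + 60. For any t ≥ 0 that is day 60 or later, beyond day 56, and for t ≥ 3 it is at or beyond day 63. With t = 7 it is day 67.

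**6. Numbers in the windows.** Assume challenges spread evenly, a stop in mid-challenge and immediate treatment.
- Over 6 months: 48/26 = 1.85 per week. Within 2 weeks of challenge: 3.7; within 6 weeks: 11.1.
- Over 8 months (22 − 14 months, or 8 × 52/12 = 34.7 weeks): 48/34.7 = 1.38 per week, giving 2.8 and 8.3.

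The range is about 3-4 and 8-11 subjects. These are people in the window, not uncured infections.

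**The case against.** A reader might infer that an infected subject can be released as cleared under any exit route. The documents do not support that. For individual leavers, 7.7 requires three negatives and requests a 60-day stool, which always falls after the stated 8-week limit for eggs. If eggs are found, a second course follows. That stool is only requested or encouraged, but subjects are free to withdraw, so some looseness is unavoidable.

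For study discontinuation, two weekly samples cannot by themselves meet the three-negative criterion, and 14.6 points to 7.7. Section 14.6 also keeps vaccinated subjects in safety follow-up and does not say that treatment is immediate. Release as cleared is therefore a possible reading of 14.6, not a rule it states. What remains is that 14.6 does not say which 7.7 schedule it means, and the standard one fits inside the same two weeks or so (step 4).

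The protocol also plainly saw the timing problem. It encourages staying to Day 189, offers follow-up to Day 297 in place of early treatment (5.3.4), and affirms a duty to offer curative therapy. The Day 189 label errs towards later treatment. These points soften the concern, but none supplies a timing relation for the four routes.

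A larger count is tempting, for example everyone within 9 weeks of challenge. It does not match the stool problem: from week 6 onward the second weekly check is already at or after week 8.

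Finally, the reference list includes a paper whose title speaks of larvicidal activity of albendazole against this species. Its content is not in the documents and nothing here rests on it, but 5.3.4 should be squared with it.

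**Conclusion.** The concern holds as an internal contradiction. The protocol states that the drug fails against immature worms and gives a maturation range, yet sets no earliest treatment time in any exit route. Its reference day is mislabelled by a week and lies inside the maturation range. Under 14.6 both clearance checks can precede the first detectable eggs (treatment before 2 weeks) or the last (before 6 weeks). That is about 4 and 11 of 48 subjects under even challenge over 6 months, a mid-challenge stop and immediate treatment, or about 3 and 8 over 8 months. For individual leavers the exposure is small if they give the 60-day stool. These are uncommon routes and no effect on the primary analysis is shown, so this is should-fix.

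**What to change.** The clinical lead must reconcile 2.1.1, 2.1.9, 5.3.4, 7.5, 7.7 and 14.6 so that every exit route relates time since challenge, treatment and clearance testing in the same way. Specifically:

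- Resolve the differing roles of Days 189, 197 and 280.
- State which 7.7 schedule 14.6 refers to.
- Reconcile the end of contraception in 2.3.1.2, exclusion criterion 2 and 14.4.
- Correct the six-week label on Day 189 and the post-CHHI labels on Days 280 and 297.
- Record time since challenge (stool date minus larval application date) with every clearance stool, so that each result can be read against the stated 4-8 week egg window.

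Which treatment time or clearance criterion is right is a clinical decision, and none is proposed here. The cost is a wording amendment and one derived variable. Sample size, endpoints and the planned analyses do not change.

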### **5.3.5 Termination of Study**

Any recommendation of the Independent Safety Monitor, DMID Medical Monitor, and SMC to resume or suspend further injections (either for an individual subject or an entire dose Group) will be communicated in writing to the sponsor and Principal Investigator. All communications from the SMC will subsequently be forwarded by the investigators to the IRB of the George Washington University.

The study Sponsor has the right to terminate this study at any time. Reasons for terminating the study may include, but are not limited to, the following:

- Incidence or severity of AEs indicating a potential health hazard
- Data recording is inaccurate or incomplete
- The Investigator has not adhered to the protocol or applicable regulatory guidelines in conducting the study

In addition, the study may be discontinued at the discretion of the U.S. FDA or the study site.

## 6 STUDY INTERVENTIONS/INVESTIGATIONAL PRODUCTS

Investigators will receive the current version of the Investigator's Brochures for Na-GST-1/Alhydrogel® (with or without AP 10-701), Na-GST-1/Alhydrogel® (with or without CpG 10104), and *Necator americanus* Larval Inoculum, which comprehensively describe all available preclinical and human experience with the experimental vaccine formulations and CHHI. If relevant new information becomes available during the course of the trial, the investigators will receive the revised Investigator's Brochure(s).

### 6.1 Study Product Description

#### Na-GST-1/Alhydrogel®

Na-GST-1 contains recombinant *N. americanus* Glutathione-S-Transferase-2 (Na-GST-1), which is expressed in modified *Pichia pastoris*. Na-GST-1 from the human hookworm *N. americanus* is a 24 kDa protein with peroxidase enzymatic activity that catalyzes the conjugation of reduced glutathione to a variety of electrophiles, including toxic compounds generated as products of blood degradation by the adult hookworm. When recombinant Na-GST-1 is used as a vaccine, it is hypothesized that it will induce neutralizing antibodies that will interfere with parasite blood-feeding and cause parasite death or reduce worm fecundity. The three formulations that will be used in this study consist of:

- (a) Na-GST-1 adsorbed to Alhydrogel®;
- (b) Na-GST-1 adsorbed to Alhydrogel® and administered with the novel immunostimulant AP 10-701, or Gluco-Pyranosylphospho-Lipid A Aqueous Formulation (GLA-AF), a synthetic lipid A molecule that is a Toll-Like Receptor (TLR)-4 agonist;
- (c) Na-GST-1 adsorbed to Alhydrogel® and administered with the novel immunostimulant CPG 10104, a synthetic oligodeoxynucleotide molecule that is a Toll-Like Receptor (TLR)-9 agonist.

